5.8.6 Safety Analysis

Safety Analysis will be performed on all patients who have at least one dose of medication on either treatment arms over the course of this study. The severity of the toxicities will be graded according to the NCI CTCAE v3.0 whenever possible. Events during the first 100 days after transplantation will be considered possibly related to the transplant for this analysis. Regimen-related toxicity will be graded and presented in a descriptive nature as incidence rates and the corresponding 95% confidence intervals.

5.8.6.1 Safety Monitoring Endpoints

The incidence of toxicities of grade 3 or higher toxicities (CTCAE version 3.0), the incidence of probable viral fungal and bacterial infections, and the incidence of treatment-related mortality, i.e., from causes other than relapse or progression, will be recorded for each patient at set intervals over the course of the study. Safety data will be described in a variety of ways, both graphical and tabular, and incidence will be compared across time points and treatment arms. The Data and Safety Monitoring Board will be presented with a comprehensive semi-annual report that will contain both solicited and unsolicited adverse event reports.

5.9 Discontinuation from study

5.9.1 Withdrawal of patients

A patient must be withdrawn from the study under the following circumstances:

- 5.9.1.1 Consent withdrawal at the patient's own request or at the request of their legally authorized representative;
- 5.9.1.2 Toxicity or adverse event requiring treatment that would, in the investigator's opinion, interfere with study endpoints
- 5.9.1.3 Safety reasons requiring discontinuation as determined by the physician(s) caring for the patient
- 5.9.1.4 Significant deviation from inclusion/exclusion criteria, in the opinion of the investigator;
- 5.9.1.5 If, in the investigator's opinion, continuation in the study could be detrimental to the patient's well-being;
- 5.9.1.6 Progression of disease (POD) after CR or PR.

When possible, subjects who are taken-off study or withdraw participation should undergo End-of-Study procedures. In addition, patients will be followed for a period of 28 days following the day of discontinuation for collection of study related adverse events.

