4.6 Follow-up of Adverse Experiences

- 4.6.1 Patients with Grade 3/4 adverse experiences will be actively followed until the event has subsided (disappeared) or until the condition has stabilized.
- 4.6.2 Adverse events, both serious and non-serious, and deaths that occur during the patient's study participation will be recorded in the source documents. All SAEs should be monitored until they are resolved or are clearly determined to be due to a patient's stable or chronic condition or intercurrent illness(es)

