5.3 Accrual, Registration and Follow-up

The targeted sample size is 54 subjects. It is estimated that four years of accrual will be necessary to enroll this number of subjects. About 50 patients (49-52) underwent allogeneic transplantation at this center, indicating that an appropriate number of subjects will be available to complete this study in the time frame anticipated. Subjects will enroll uniformly over the accrual period. The randomization will be stratified by relapse risk status (high versus low). Low relapse will include: AML CR1 and CML chronic phase. All other AML, MPD and MDS patients will be considered high relapse risk. An AML CR1 patient with a history of MDS will be considered high relapse risk. All patients who are Flt3/ITD positive at any time will be considered high relapse risk. Upon establishing eligibility, subjects will be randomized in equal numbers to the FluBu and FluBuTBI arms using permuted blocks within strata.

All subjects will be followed for one year from time of transplantation, during which they will be monitored for the effects of treatment through regular clinic visits. Additional follow-up data beyond one year of progression-free survival will be obtained from HUMC Cancer Center Database.

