5.8.2 Overall Survival

The event is death from any cause. The time to this event is the time from randomization to death, loss to follow-up or the end of the study, whichever comes first. Patients alive at the time of last observation are considered censored. The Kaplan-Meier estimate of survival will be estimated separately for each treatment-

group and risk status. A log-rank test stratified on risk status, conducted at a one-sided significance level of 0.05 analogous to the analysis of relapse risk described above.

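### Section 5.9.1 withdraws patients from the study at progression while Sections 3.1 and 5.3 follow everyone for one year; whether deaths after withdrawal count toward overall survival is not settled

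*Combined protocol and SAP*

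**What the plan says.** Section 5.9.1 is worded as an obligation: "A patient must be withdrawn from the study under the following circumstances". Item 5.9.1.6 of that list is "Progression of disease (POD) after CR or PR". For what follows, the section says that, when possible, "subjects who are taken-off study or withdraw participation should undergo End-of-Study procedures", and that "patients will be followed for a period of 28 days following the day of discontinuation for collection of study related adverse events". Section 5.9.2 also treats disease progression as a reason for discontinuing, since such patients are not to be replaced.

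Section 5.3 says "All subjects will be followed for one year from time of transplantation", with no exception for withdrawn patients, and Section 3.1 likewise follows subjects to one year. Section 5.3 adds a later source: "Additional follow-up data beyond one year of progression-free survival will be obtained from HUMC Cancer Center Database".

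On deaths, Section 4.6.2 says "deaths that occur during the patient's study participation will be recorded in the source documents". Section 5.8.2 defines OS by "The time to this event is the time from randomization to death, loss to follow-up or the end of the study, whichever comes first" and censors living patients when last observed. It does not mention withdrawal. Sections 5.2.1 and 5.8.1.2 instead start OS at the first dose.

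**The concern.** The randomized conditioning is finished by the day of transplant, so withdrawal at a later progression can only affect follow-up. If observation stops shortly after relapse, OS is censored just when the risk of death rises. That censoring is informative. It would also be more frequent in the arm that relapses more, which the plan expects to be FluBu.

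At stake are OS and the overall-mortality models of Section 5.8.5, all secondary. They still matter, because Section 5.1 censors deaths without relapse in the primary endpoint. OS is therefore one of the few tested comparisons that show whether fewer relapses outweigh any added mortality from TBI.

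**Working it through.** **The passages side by side**

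- After progression, 5.9.1 takes the patient off study, with safety collection for 28 days.
- 3.1 and 5.3 keep the patient under follow-up to one year.
- 4.6.2 ties the recording of deaths to study participation, which 5.9.1 ends.
- The database in 5.3 is named for data beyond one year of progression-free survival, not for vital status in year 1 after a relapse.
- 5.8.2 censors at last observation but does not say when that falls for a withdrawn patient.

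Two analysts could follow this text and obtain different OS data.

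**The plan's own figure**

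The plan gives no power for OS. Its only power figure is 80.06% for relapse (Section 5.4: 52 patients, one-sided 5%, 4-year accrual, 1-year follow-up, 10% dropout). With constant hazards:

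- HR = ln(0.864)/ln(0.66) = 0.352, and expected events are 23.3.
- Schoenfeld power = Φ(√23.3/2 × |ln 0.352| − 1.645) = 80.9%. A Lakatos-type grid gives 79.1%.

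The figure is reproduced within about a point, which supports using constant hazards below.

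**Inputs for the illustration**

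- From the plan: one-year relapse 34% and 13.6%; 27 per arm (5.4).
- Assumed: one-year non-relapse mortality (NRM) of 10% in both arms. Section 5.10 gives 10% for FluBu beside a 3-month rule and no rate for FluBuTBI.
- Assumed: median survival after relapse of 6 months (range 3 to 9).
- Assumed: 100%, 75% or 50% of relapses trigger withdrawal. The trigger needs a prior CR or PR, Section 3.2.1.2 admits any disease stage, and the qualifying share is not given.
- Assumed: observation ends at relapse + 28 days.

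At most 27 × 0.34 = 9.2 FluBu and 27 × 0.136 = 3.7 FluBuTBI patients would be withdrawn at relapse, a ratio of 2.5 to 1.

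**One-year OS with full follow-up**

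Let λ = −ln(1 − relapse), κ = −ln(0.9) = 0.1054, μ = ln 2/0.5 = 1.386 and a = λ + κ. Then S(1) = e^(−a) + λ(e^(−μ) − e^(−a))/(a − μ).

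- FluBu: λ = 0.4155, e^(−a) = 0.66 × 0.9 = 0.594. S = 0.594 + 0.4155 × (0.25 − 0.594)/(0.521 − 1.386) = 75.9%.
- FluBuTBI: λ = 0.1462, e^(−a) = 0.864 × 0.9 = 0.7776. S = 0.7776 + 0.1462 × (0.25 − 0.7776)/(0.2515 − 1.386) = 84.6%.
- Unrounded difference: +8.6 points.

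**One-year OS with censoring at relapse + 28 days**

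The large-sample Kaplan-Meier value is exp(−∫h(s)ds) over 0 to 1, with h = (κE + μP)/(E + P). E is the relapse-free proportion, and P the proportion relapsed, alive and still observed. If all relapses trigger, the arms read 86.7% v 88.8%; if half do, 80.7% v 86.6%. OS difference (FluBuTBI minus FluBu), in points:

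| Median survival after relapse | Full follow-up | All trigger | 75% trigger | Half trigger |
|---|---|---|---|---|
| 3 months | +12.7 | +4.0 | +6.7 | +9.0 |
| 6 months | +8.6 | +2.1 | +4.1 | +5.9 |
| 9 months | +6.3 | +1.4 | +2.9 | +4.3 |

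Standard error of the difference at 27 per arm: √(0.759 × 0.241/27 + 0.846 × 0.154/27) = 10.8 points.

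**Equal relapse**

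With 34% relapse in both arms, OS rises from about 76% to 87% in each arm if all trigger, and the difference is not distorted. Simulated one-sided rejection stays near 5% (5.2% with full follow-up, 5.0% with censoring).

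**Power of the OS test**

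Simulated with an unstratified one-sided 5% log-rank test (stratum shares are not given), 27 per arm, 6-month median:

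| Horizon | Full | All trigger | Half trigger |
|---|---|---|---|
| Cut at one year from transplant | about 20% | about 8% | about 14% |
| To one year after accrual ends (1 to 5 years each) | about 49% | about 10% | about 31% |

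Sections 5.7 and 5.8.2 point to the second horizon; the follow-up sentence in 5.3 points to the first.

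**The case against.** A reader might infer that the plan censors OS at relapse, or that it provides no survival follow-up after withdrawal. The documents support neither. Sections 3.1 and 5.3 cover subjects to one year without exception, and 5.8.2 does not name withdrawal as a reason to censor. The 28 days are a safety-reporting window, added to the other procedures and not stated to be the last contact for vital status. Section 4.6.2 sits in the adverse-event chapter and concerns source recording. One can reasonably read withdrawal as ending protocol participation while OS follow-up continues. This stands: relapse + 28 days is one literal reading, and the magnitudes depend on it.

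It also stands that the imbalance needs a real relapse difference, that survival after relapse and the triggering share are not in the documents, and that the shift at the 6-month median (2.8 to 6.5 points) is smaller than the standard error.

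The objection does not remove the conflict. The 5.9.1 rule is mandatory and concerns the study, not treatment. Site staff following it could stop contact, and deaths missed for that reason cannot be restored by the analysis.

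**Conclusion.** The contradiction is certain from the text. Its effect on OS is conditional. If 3.1 and 5.3 govern, there is none. If 5.9.1 is applied literally, OS is overstated in both arms; with the planned relapse rates more deaths are hidden in FluBu, and the difference shrinks toward zero. Under the 6-month assumptions it falls from +8.6 to between +2.1 and +5.9 points. This is bias in an already imprecise secondary estimate, worth correcting because the remedy is cheap.

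Three stronger inferences are not supported:

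- **Bias in the primary endpoint.** Progression is already the event in 5.1 and in the event-free survival of 5.8.4, so item 5.9.1.6 leaves both intact. Withdrawals under 5.9.1.2 to 5.9.1.5 could end relapse follow-up early for patients whom 5.7 keeps in the primary analysis; the size of that was not estimated.
- **A falsely positive OS result.** With equal relapse and equal NRM, rejection stays near 5%.
- **A reversed OS result.** At equal NRM the sign does not change; a reversal needs an assumed excess of NRM with TBI.

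The OS time origin (first dose in 5.2.1 and 5.8.1.2, randomization in 5.8.2) is a separate inconsistency in the same endpoint.

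**What to change.** Reconcile 5.9.1 with 3.1 and 5.3. State in 5.9.1 that withdrawal ends protocol participation but not outcome follow-up. Collect vital status to at least one year for every randomized patient, and relapse status for those withdrawn before relapse, unless the patient withdraws consent to follow-up. State in 5.8.2 that withdrawal alone does not censor OS, and give the OS data cut-off. Use randomization as the single OS origin in 5.2.1, 5.8.1.2 and 5.8.2, to match the intent-to-treat comparison. If power for OS is quoted, give its horizon.

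The cost is protocol wording plus a vital-status and, before relapse, disease-status check for withdrawn patients at one centre. Sample size and treatment do not change.

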5.9.2 Replacement of patients

Patients withdrawn after treatment group assignment may be replaced unless the patient discontinued due to an adverse event or the patient met a study endpoint (e.g., disease progression).

5.10 Stopping Rules

If the non-relapse mortality rate in the experimental group receiving TBI within the first 3 month post exceeds 20% then the study will be stopped. It is assumed that the NRM in the standard FluBu conditioning regimen is 10%. Resumption of patient accrual will only be permitted after review of interim results by the Institutional Review Board and the Data Safety Monitoring Board

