The fludarabine, busulfan, TBI (FluBuTBI) regimen has been established in an effort to reduce the relapse rate (9). Russell et al. evaluated a myeloablative regimen of daily busulfan, fludarabine, and 400 cGy total-body irradiation given before allogeneic transplantation. Sixty-four adults with acute leukemia in first and second remission were evaluated. All patients also received ATG. For 31 matched related and 33 alternate donor stem cell transplantation the overall treatment-related mortality was 3%. Projected disease-free and overall survival at 3 years for AML were the same at 83%, and for acute lymphoblastic leukemia were 65% and 78% respectively. For the matched related donors

the disease free survival was 77% and overall survival 87%, for alternative donors the disease free survival and overall survival were 71% and 84% respectively. Overall survival and disease free survival in patients without and with high-risk features were 100% versus 71% and 88% versus 68%, respectively. This combination therefore appears to be well tolerated and may offer better disease control than the standard FluBu.

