6.3 Data and Safety Monitoring Board

The HUMC DSMB is responsible for developing and enacting procedures to monitor safety of participants in protocols that it oversees. They provide multidisciplinary, independent oversight of research studies conducted by HUMC staff and or affiliates, focusing on assuring integrity of research and safety of subjects. The DSMB has the ability to require protocol modifications related to participant safety and to recommend suspension or termination to the IRB and institutional official of any research protocols that fall within its jurisdiction. The DSMB may request that HUMC's Corporate Compliance Department to conduct a periodic audit to assure that data are being collected and recorded according to the protocol. The investigator will submit monitoring reports that include current enrollment data, adverse event summary data, and any other data requested by the DSMB.

The DSMB will meet monthly to review the trial progress, adverse event data, and any relevant information such as significant amendments or reviews from IRB submitted by the principal investigator.

7 References:

1. Müller CT et al.: DNA methylation of myeloid cells, a novel therapeutic target in MDS and AML.
2. Martin S et al.: Defective neutrophil function and microbial mechanisms in myelodysplastic syndromes. *J Clin Pathology* 36:1120, 1983.
3. Martino R. et al.: Retrospective comparison of reduced-intensity conditioning and conventional high-dose conditioning for allogeneic hematopoietic stem cell transplantation using HLA-identical sibling donors in myelodysplastic syndromes. *Blood*, 1 Aug. 2006, Vol 108, N.3 pp 836-846.
4. Fukuda T et al.: Risks and Outcome of idiopathic pneumonia syndrome after non-myeloablative and conventional conditioning regimens for allogeneic hematopoietic stem cell transplantation. *Blood*. 2003; 102:2777-2785.
5. Diaconis R. et al.: Morbidity and mortality with non-myeloablative conditioning before hematopoietic cell transplantation from HLA-matched related donors. *Blood*. 2004; 104:1550-1558.
6. DeLima M, et al.: Nonablative versus reduced-intensity conditioning regimens in the treatment of acute myeloid leukemia and high-risk myelodysplastic syndrome: dose is relevant for long-term disease control after allogeneic hematopoietic stem cell transplantation. *Blood*. 2004; 104:865-872.

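### Does the 20% non-relapse mortality stopping rule need a denominator, a minimum number of patients and a look schedule?

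*Combined protocol and SAP*

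**What the plan says.** Section 5.10 (Stopping Rules) is the whole rule. It names the arm, the window and the threshold: "If the non-relapse mortality rate in the experimental group receiving TBI within the first 3 month post exceeds 20% then the study will be stopped". The section gives a reference rate, "It is assumed that the NRM in the standard FluBu conditioning regimen is 10" per cent, and says what happens after a crossing: "Resumption of patient accrual will only be permitted after review of interim results by the Institutional Review Board and the Data Safety Monitoring Board".

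Two other sections bear on it without referring to it. Section 5.8.6.1 says that "the incidence of treatment-related mortality, i.e., from causes other than relapse or progression, will be recorded for each patient at set intervals", and that "The Data and Safety Monitoring Board will be presented with a comprehensive semi-annual report". Section 6.3 says "The DSMB will meet monthly to review the trial progress", and gives the board the power "to recommend suspension or termination to the IRB and institutional official of any research protocols" within its jurisdiction.

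No section states a minimum number of patients, the denominator, the times at which the rule is applied, or the chance of a suspension at any true rate.

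**The concern.** The rule compares a raw proportion with a fixed percentage, and in a small arm such a comparison is unstable at the start. Read literally from the first patient, one non-relapse death among the first four TBI patients crosses it. The exact 95% interval for 1 death in 4 runs from 0.6% to 81%, so that crossing says little about the true rate.

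The denominator is open as well. It could be all transplanted patients, those who completed 3 months, or those who completed 3 months or died. Sections 5.9.1 and 5.9.2 allow withdrawal and replacement without saying how such patients count here. The semi-annual report and the monthly meetings are different rhythms, and neither is tied to the rule. The 10% reference rate carries no explicit time window.

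If this mattered, the IRB and DSMB could not tell from the text how often accrual would be halted at an acceptable NRM, or how quickly a high NRM would be caught. Denominator and timing might also be chosen after deaths are known.

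**Working it through.** **Inputs.** Threshold: observed rate above 20% (5.10). Reference rate: 10% (5.10). TBI arm: 27 patients (5.4). Accrual: 54 patients, uniformly over 4 years (5.3, 5.4), so 54/48 = 1.1 per month, about 0.56 of them in the TBI arm.

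**The plan's own figure.** Section 5.10 states no operating characteristic, so there is none to reproduce. The arm size rests on the power calculation in 5.4 (52 patients, 80.06%). With exponential hazards from 34% and 13.6%, 4 years of accrual, 1 year of follow-up, 10% loss per year and one-sided 5%, the Schoenfeld formula gives 80.9% and a Lakatos-type calculation 79.1%. The arm size is not in dispute.

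**One final look.** 5/27 = 18.5% does not exceed 20%; 6/27 = 22.2% does. P(X ≥ 6), with X binomial(27, 0.10), is 4.7%. At 20% true NRM it is 46.1%.

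**Looks after each patient.** Exact recursion on the binomial path, suspending at the first n with k/n > 0.20:

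| True 3-month NRM | Chance of a suspension |
|---|---|
| 3% | 12% |
| 5% | 21% |
| 10% | 43.5% |
| 12% | 52% |
| 20% | 81% |
| 30% | 97% |

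One death in four is 25% and crosses; one in five is exactly 20% and does not. At 10% NRM the first four patients alone contribute 1 − 0.9⁴ = 34.4 of the 43.5 percentage points.

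**Monthly looks (the meeting rhythm in 6.3).** Simulation at 10% NRM, assuming random uniform entry over 48 months and deaths spread evenly over 3 months: 37.1% with all transplanted patients in the denominator, 42.1% with those who completed 3 months, 46.7% with those who died or completed 3 months. At 20% NRM the range is 77-83%.

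**Six-monthly looks (the report rhythm in 5.8.6.1).** At 10% NRM the exact recursion gives 27.6% with looks at n = 1, 5, 8, 11, 15, 18, 21, 25, 27 and 41.5% with looks at n = 1, 4, 7, 11, 14, 18, 21, 24, 27. Simulation with evenly spaced entry widens this to 22-43%. A single death causes 36% of suspensions on the first of those schedules and 77% on the second. The picture of a pause triggered mostly by one early death therefore holds for monthly or per-patient looks, but not across the six-monthly range.

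**What a minimum would buy.** The same 20% threshold, applied only from the fifth TBI patient:

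| Looks | NRM | As written | From n = 5 |
|---|---|---|---|
| Each patient | 10% | 43.5% | 28.6% |
| Six-monthly, first schedule | 10% | 27.6% | 23.3% |
| Six-monthly, second schedule | 10% | 41.5% | 24.4% |
| Each patient, by 10 patients | 20% | 70% | 56% |
| Each patient, by 10 patients | 30% | 87% | 80% |

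The first three rows show fewer pauses at the reference rate, in one case by only about 4 points. The last two show the price: slower detection when mortality is high. No number of deaths among the first four patients would trigger the formal rule.

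**The case for a change.** The strongest case for a change is that one rule, read in ways the text equally permits, gives false-suspension rates from 4.7% to 47%. At the late end it crosses only 46% of the time when true NRM is 20%, and only after all 27 patients have been irradiated. On this view, writing down denominator and look times costs a few sentences and prevents choices made after the deaths are known.

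Part of this stands: the definitions are missing, and the spread is genuine. The weight does not.

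- The single late look is a remote reading. Section 5.10 speaks of resuming accrual, so the rule is meant to operate during accrual, and the board meets monthly.
- The 47% is the top of a 37-47% range and needs one particular denominator.
- The 10% follows directly on a sentence limited to the first 3 months, so the same window is the natural reading. A threshold of twice the reference rate is a plausible rationale, though unstated.
- The 10% is the assumption for FluBu. The only FluBuTBI result in the documents (section 1.2) is that "the overall treatment-related mortality was 3" per cent, in a narrower population. At that rate the two six-monthly schedules suspend in 5-12% of trials. At the 12% that section 1.2 reports for FluBu they suspend in 36-50%, so the lower figure cannot be relied on alone.

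**Conclusion.** No change to the plan follows. Section 5.10 leaves its denominator, first look and timing unwritten, and at 10% true NRM the chance of a suspension is about 22-43% at the six-monthly rhythm and 37-47% at the monthly one. The only consequence is a reviewable pause. It does not end the trial or bias the primary comparison, and at 1.1 patients per month each month of pause delays about one enrolment.

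The board that meets monthly can settle who counts and when, and it can recommend suspension whether or not the formal rule is crossed. Writing the definitions down would be tidy, but would leave the choice of boundary with the same board. An early, sensitive trigger is a defensible cautious choice when an arm adds irradiation to a standard regimen. Damping it lowers suspension by ten patients from 70% to 56% at 20% NRM, and that is a judgement rather than a correction.

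The figures assume 27 TBI patients and independent outcomes. The simulations also assume deaths spread evenly over 3 months and entry over 48 months. The length of an IRB and DSMB review is not stated, so the total delay cannot be given.
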